7.1.5 Recruiting participating SMEs and randomisation of sites to control or intervention group

The three participating LEOs will each help us to recruit between six and eight SMEs seeking to improve their HWS provision in their supply chain to participate in the study. We will aim for eight SMEs per LEO, but acknowledge we may have difficulty recruiting the full complement across all supply chains. If it not deemed feasible to recruit eight SMEs in an LEO, we will accept a minimum of six SMEs, which should still allow for adequate power for our study (see Section 8.1.6 – Power calculation). A maximum four-month window period will be used to identify and recruit the 18-24 SMEs (six to eight SMEs from each of LEO supply chain) into the study during the pre-randomisation stage. Those who are interested will be told to contact the research team. We will set up a meeting with each interested SME to ensure that they are eligible for the study, to explain the study to them and answer any questions they may have, and to share a provisional version of the study contracts with them. If all are satisfactory and the SME consents to participate in the study, the study team will collect data about the workforce demography and size of each SME.

In late November/early December 2025, randomisation will occur (assigning SMEs to intervention or control arm). We would ideally randomise all eight SMEs per LEO together, however, we will conduct the first randomisation in each LEO at this time if a minimum of four SMEs have been recruited. We will then begin to roll-out the study in these randomised SMEs, and continue to recruit additional companies in background, which we can then randomise at a later point and who would have a slightly delayed beginning for the study/HWS intervention. Therefore, randomisation may occur at six separate time periods (twice for each LEO), ensuring there are no delays in the randomisation and delivery of the intervention from each LEO. There will be no more than a month or two between the staggered beginning of the study roll-out in SMEs within each LEO. We will endeavour to recruit even numbers of SMEs for each LEO to ensure that half of all participating sites are in the intervention arm and half are in the control arm. Randomisation will be undertaken by a co-investigator who is not involved in recruiting or working directly with the SMEs (likely [name] - University of Leeds).

Prior to randomisation, and if possible, we will match SMEs within each LEO by workforce size (i.e., the companies with the two highest workforce sizes will be matched, then SMEs with the 3rd and 4th highest workforce size will be matched, and so on). SMEs will then be randomised within each of these pairings. This will help us to ensure that our intervention and control arms are balanced for size, considering some SMEs may have 200+ employees while others may have 10-20. As above, we will aim to randomise all SMEs per LEO at the same time, however, to avoid potential delays, we will conduct the first randomisation with a minimum of four SMEs if appropriate. In this event, we will pair and randomise the SMEs that we have already recruited, continue working to recruit new SMEs, and then we will pair the new SMEs in the same manner and then randomise them within their pairings, via a second randomisation.

Each organisation will be assigned an ID and paired by LEO and workforce size by Affinity, and the IDs will be provided on an excel sheet to [name] so he is blind to organisation name. [name] will then randomly allocate the paired organisations into either the control or intervention group. He will put the outcome of the randomisation process for each organisation on the excel sheet and send it back to Affinity. These will result in 3/4 SMEs in the intervention group and 3/4 in the control group for each LEO (9-12 in intervention and 9-12 in control overall). Affinity will notify the SMEs of the outcome of the randomisation process. Each envelope will be opened in a recorded Teams meeting with others present from Affinity and GST to ensure transparency, and the recording will be stored in GST files.

Once intervention and control SMEs are identified, inception meetings will be held for each SME we which we will include the LEO, the SME's management team and the research team to establish the implementation and research requirements. Following SME director/owner commitment, arrangements will be made with intervention and control arm SMEs to set up the study.

Intervention SMEs will establish a working group to work with the research team to simplify the HWS package for implementation, determine delivery methods, and plan evaluation procedures.

The control SMEs will also make arrangements for data collection (administration of surveys) and mechanism for seeking feedback.

7.1.6 Recruitment of health champions

Within each intervention SME, at least two volunteer champions will be recruited internally via an expression of interest process. Role specifications for champions will be provided by the research team drawing on insights from the MHPP project for their role specification. Specifically, we will ask a senior HR/management team member at each intervention SME to share information about the champion role with employees that they feel would be suitable. Those who are interested will then be able to contact the research team to express their interest. Should more than two people in any SME express an interest in the role, we will work with the SME management to decide on which two people should be chosen for the role. Supported by a senior HR/management member, champions will dedicate work hours to fulfil the dual role of acting as natural helpers in intervention delivery and liaising with the research team to capture implementation insights.

Champions will receive training in principles of health and work including health promotion, return to work, behaviour change and communication skills. Delivered by a Health and Wellbeing Advisor (hereafter referred to as 'advisor') who specialises in workplace interventions, this training will equip champions to facilitate health-promoting activities. Champions will be invited to join a monthly "Community of Practice" meeting [23] alongside peers from other SMEs, facilitated by the advisor. Additionally, to safeguard the champions' own health and wellbeing, champions will have the opportunity to contact the advisor throughout the study for support and advice regarding the implementation of the HWS intervention. Records of these interactions will inform the process evaluation.

Informed by research with SMEs, proposed measures will undergo assessment by SME employees and employers from the ESPG. The questionnaires, tailored to preferences, will

be either paper based or on-line. We'll ask SMEs if we can access and use routinely collected data relevant to employee engagement, health and productivity. While this may not be consistently available, gathered data may be used in cost-effectiveness assessments.

7.1.7 Output (2):

- i) Finalise the study intervention characteristics and mode of delivery
- ii) Prepare SMEs for intervention implementation including training SME 'health and wellbeing champions'
- iii) Finalise data collection tools and draft study questionnaire.

The study activities described above and undertaken within WP 1 fall within the definition of a 'service evaluation'.

7.1.8 DATA

Data to be collected

Qualitative data

1. An interview guide will be used to facilitate the qualitative data collection. Interviews will be conducted either in-person or virtual based on local preferences. Interviews will be recorded with permission. Audio data will be transcribed verbatim and automatically generated using Microsoft Teams. As part of data cleaning, the transcripts will be compared with the audio files to ensure data quality assurance. Interviewers will also type notes during/after interview.

Organisational data, policies and HWS material for LEOs and organisational data from SMEs

2. Organisational policies, data exports, existing reports, employee communications and field notes on use and evaluation of HWS will be requested from participating LEOs and used to collate organisational data for review and analyses. This information will be used to inform which components of HWS are offered to SMEs and how these HWS are communicated to SME employees.

A range of documents, reports and data will be requested from LEOs as part of the review exercise including:

- documents outlining the LEO's priorities and operations around health and wellbeing (e.g. health and wellbeing strategy, risk assessments, health/wellbeing department structure chart)
- policies on health and wellbeing (e.g. sickness absence policy, flexible working policy)
- documents outlining the development, design and delivery of HWS, including how they are communicated and accessed by staff (e.g. map of services, theoretical underpinnings, referral systems, promotion posters/emails)
- evaluation reports and/or data on the reach, impact and implementation of HWS
- contextual anonymised organisational data on staff health and wellbeing (e.g. employee mental wellbeing, no. near misses/accidents, on sickness absence).

LEO contacts will also be asked to complete an onboarding excel spreadsheet asking for organisational demographics (e.g. size, type of work, main hazards, whether policy and practice documents listed above are in place, type of services run by their OH/wellbeing department).

SMEs that consent to take part in the study will be asked to complete a short onboarding document on the size of their organisation, length of operation, length of contracting with LEO, sector, type of work, main hazards in place and use of OH services. Where available they will also be asked to provide policies on health and wellbeing (e.g. sickness absence policy) and organisational data or reports on staff health and wellbeing (e.g. employee mental wellbeing, sickness absence rate).

2. Data handling and record keeping

Qualitative data

1. The study team will not disclose or use for any purpose other than performance of the study, any data, record, or other unpublished confidential information disclosed to those individuals for the purpose of the study. Prior written agreement from the Host or its designee will be obtained for the disclosure of any said confidential information to other parties.

Digital recordings of interviews will be made using a Dictaphone device (for telephone and in-person interviews) or Microsoft Teams (for online interviews) and transcribed within Microsoft Teams. Files will be downloaded and securely stored at Affinity Health at Work only on a password protected shared drive, with limited access by the authorised study staff only. Recordings and transcriptions made on Teams will be immediately deleted from the Microsoft Cloud once they have been securely downloaded. The saved transcripts will be pseudonymised and identified by unique participant IDs and a member of the Affinity research team will check the transcript for clarity and accuracy. The recorded interview will then be deleted soon after transcription has been checked. Audio files created on an encrypted Dictaphone will be sent via upload to a cloud-based depository portal and processed by Accuro, an external transcription service approved by the Guy's and St Thomas NHS Foundation Trust. Recordings will be immediately deleted after the transcription has been completed.

Data storage procedures will follow Affinity Health at Work standard operating procedures for research.

All the information/data collected for this study from participants will be securely stored in folders on the Affinity Health at Work secure servers, folders will be password protected and can only be accessed by the research team. The recording equipment used to record the interviews will be erased after each interview has been uploaded to the secure folder on the Affinity Health at Work server. The pseudonymised interview recording, pseudonymised transcripts, and the consent form with identifiable personal information, will be stored in separate locked and protected folders on Affinity Health at Work secure servers in line with GDPR requirements for the duration of the study. Each file will have the unique study ID for each participant, and it will only be possible to identify the participant by looking at the consent form and linking this study ID to the other documents. Data will remain pseudonymised to allow participants to withdraw their data from the study, should they desire. The protocol for withdrawing data will be explained to participants in the PIS.

All qualitative data collected will not be stored with any identifying information. A code number will be allocated to each qualitative participant and will be stored securely, to ensure that participants cannot be identified from their response.

Affinity Health at Work will be the data processor for this qualitative work, working on behalf of Guy's and St Thomas' NHS Foundation Trust as the data controller, and responsible for looking after the information and using it properly.

Data will only be held where there is a legitimate need to do so. Once the stage of the study which involves inviting participants to take part in research and asking for their express consent is complete the contact details will be securely destroyed.

All data will be retained for two years after the end of the research study as per GSTT guidance before being destroyed (deleted electronically).

2. Organisational data and documentation

Affinity Health at Work will be the data processor for the organisational data and documentation, working on behalf of Guy's and St Thomas' NHS Foundation Trust as the data controller, and is responsible for looking after the information and using it properly. Data storage procedures will follow Affinity Health at Work standard operating procedures for research. All data will be retained for two years after the end of the research study as per GSTT guidance before being destroyed (deleted electronically).

7.5 Data Sharing

The data generated by this work package will be created and stored at Affinity Health at Work, as they are operating as a Data Processor on behalf of GSTT.

The only components of the work package that will be stored within GSTT will be the finalised analysis report of the qualitative interview data. The completed consent forms will be transferred from Affinity Health at Work to GSTT for the purposes of archiving, and the analysis report will contain only pseudonymized data about the participants who completed interviews. Other outputs from the qualitative interview analysis other than the analysis report (i.e. annotated transcripts, etc) will be retained at Affinity Health at Work.

At the end of the study and with consent from participants, the final anonymised dataset will be uploaded to OSF (a publicly accessible) data repository for future ethically approved research. This has been highlighted on the PIS and the ICF, and participants will have the option to with-hold their anonymised data if they desire.

A full description of the data flow is provided in the study's Data Protection Impact Assessment document.

8 Phase 2: Implementation

8.1 Work Package 2: Implementation of the HWS intervention in SMEs within supply chains (Leads: JY/VP/AS)

8.1.1 Objectives:

- i) To implement the multi-component model of HWS in SMEs within the supply chain of LEOs. (WP2)

8.1.2 Description of the intervention

Each supply chain SME will receive a bespoke HWS intervention which has been specially designed and tailored to their specific needs and requirements. This HWS intervention will be a package of individual components which will include as a minimum: workplace health awareness, health promotion, prevention of mental ill health and training managers to have work and health conversations with their teams. The individual components included in the HWS intervention for each supply chain SME will be developed based on: (1) a review of the existing HWS within each participating LEO to ensure that the individual components are designed and delivered in accordance to good practice and can be delivered safely and with fidelity in an SME context and (2) the needs of each supply chain SME, appreciating that each SME may have some existing HWS in place. The exact Health and Wellbeing Support (HWS) offered to each SME will depend on the HWS available at the Local Enterprise Organisation (LEO) they work with, and will be advertised to staff locally in the workplace before and throughout the intervention. As the protocol was submitted for ethical review prior to finalising the HWS with participating LEOs and SMEs, the specific interventions to be implemented are not described in detail here. However, any new HWS interventions not currently described in this protocol will be submitted for ethical approval as an amendment prior to implementation.

The development of each HWS intervention will be also consider coverage of i) levels of control [22] (Lecours et al., 2024); ii) levels of intervention target (including individual, group, leader, organisation; Yarker et al., 2024); and iii) guided by the Society of Occupational Medicine's buyers guide for health and wellbeing products and services (Yarker et al., 2024).

It is likely that several delivery channels will be incorporated including:

- access to self-guided resources, accessed via web, intranets or in hard copy
- all staff webinars with question and answer opportunities
- tailored expert-led training sessions facilitated by work and health experts, delivered to all staff or specific staff groups (eg. Hand arm vibration for estates workers, male mental health for men, leaders)

To promote intervention delivery, 'health and wellbeing champions' from each SME in the intervention group will be trained and supported to develop bespoke communication material to raise awareness of available HWS services on offer from the LEO to their SME workforce and will coordinate targeted engagement activities for the HWS intervention as a whole package and the specific individual components. This will also include champions facilitating work and health conversations with individuals in the workplace.

In the intervention group, the duration of the intervention delivery will be 12 months.

8.1.3 Control arm (Comparator)

Control arm SMEs will not receive the intervention. However, in order to provide some form of compensation and incentive to take part in the study, control arm SMEs will receive the same summary data reports following data collection, and champion training post-study evaluations, that are also provided to the intervention group SMEs. These reports offer insights into the workforce's health and wellbeing, along with recommendations for independent, future action on employee health and wellbeing. To limit the risk that employee outcome survey responses are influenced by these summary data reports (contamination

[figure not shown]
effects), they will be provided to control arm SMEs after the employee survey has been conducted at each time point (baseline, 6, 12 and 18 months). This approach has been successfully applied in the NIHR-funded IGLOO study to secure engagement from control organisations. Additionally, once all study data has been gathered, control SMEs will also be invited to nominate an employee for work and health training to transfer new knowledge and skills into the control SMEs.

Together, these services would otherwise cost at least £5,000 per SME, representing an attractive financial offer to control SMEs.

8.1.4 Masking & other measures taken to avoid bias

As referred to above, upon consenting into the study, SMEs will be randomly allocated to intervention or control arms by a member of the research team who has had no prior interaction with the employees at any SME. Prior to randomisation, we will match SMEs within each LEO by workforce size (i.e., the companies with the two highest workforce sizes will be matched, then with the 3rd and 4th highest workforce size will be matched, and so on). SMEs within each of these pairings will then be randomised. This will help us to ensure that our intervention and control arms are balanced for size, considering some SMEs may have 200+ employees while others may have 10-20. Due to the nature of the intervention, it is not possible to blind participants in the LEOs and SMEs to their group allocation. Companies will be informed of the allocation soon after consenting for their involvement in the study prior to consent.

8.1.5 STUDY FLOW DIAGRAM (INTERVENTION and CONTROL ARM)

8.1.6 Participant Selection

Participants recruited into the study will be drawn from the 18-24 SMEs recruited to take part in the study and we will work with the local collaborator at each SME to develop an acceptable method to invite participants to take part. We will monitor recruitment from each participating centre and will relay information back to the local sites, so they are aware of the recruitment uptake.

Sample size calculation and justification

A previous study of a workplace intervention to build and sustain work engagement [27] suggests a mean (SD) work engagement score of 5.08 (1.40) in the control and 5.76 (0.86) in the intervention group. As the proposed intervention is SME-based, sample size calculations must account for clustering effects. With the rho of 0.1 and the above values for expected change in work engagement scores, seven SMEs per intervention arm ensure 90% power at a 5% significance level (2-sided) to detect differences in the primary outcome. To account for participant attrition, we plan to over-sample with nine to twelve SMEs per arm, depending on the availability of interested SMEs, and to maximise the recruited employee sample per SME.

Given the workforce size of SMEs (between 10 and 249 employees), and assuming a uniform response rate across the recruited SMEs no greater than 50%, the anticipated number of participating employees per SME will range from 5 to 125, equivalent to an average of 65 employees per SME. Put together, the anticipated sample size across the minimum of 18 recruited SMEs would be 1170 employees, rising to 1560 employees if we can recruit the full complement of 24 SMEs. This ensures robustness in detecting meaningful changes in work engagement attributable to the proposed intervention.

8.1.7 Participant inclusion criteria

This study will be implemented at an organisational-level and so all employees at participating SMEs will be eligible to take part in the study. We anticipate this will include salaried employees and others that SMEs deem appropriate to involve, e.g. those undertaking apprenticeships. All participants will be of working age, i.e. 16+ years).

8.1.8 Participant exclusion criteria

Persons aged under 16 years.

8.1.9 Study Procedures:

Screening procedure

On behalf of the research team, the local collaborator and champions (intervention sites) at each of the participating SME organisations will disseminate study promotional material (invitation letter) and participant information sheet (PIS) in either an email or in paper format (depending on their preference) to all employees at least 7 days before the participant recruitment period commenced. The invitation letter and PIS will be co-designed and co-signed by our ESPG, which we anticipate will assist in optimising the participant recruitment rates. The PIS will include an overview of the study, with the contact information for the research team should individuals have any questions or require further clarifying information. Additionally, a study poster or other promotional material (flyer) will also be displayed within the workplace setting to promote the study locally.

Participant recruitment

Participants who are interested in taking part in the study will be directed to complete informed consent via REDCap (database form 1). For those who choose to complete an online survey, we will enable a setting in REDCap that will send participants an email reminding them about the survey and providing a link to it if they have not completed it within a set period of time after completing the consent form. We will send participants a maximum of two follow-ups; the first 48 hours after they completed the consent form and the second one week after they completed the consent form. A paper study pack containing the consent form and questionnaire will also be made available upon request.

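### Employees are recruited and surveyed at baseline after their SME's allocation is known, with champions helping to invite in one arm only: a risk of arm-dependent recruitment

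*Protocol*

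**What the plan says.** Section 7.1.5 sets the order at SME level. SMEs consent, are paired by size within LEO, and are randomised. Then "Affinity will notify the SMEs of the outcome of the randomisation process". Set-up comes next: "Once intervention and control SMEs are identified, inception meetings will be held for each SME". The survey is still to be arranged at that point: "The control SMEs will also make arrangements for data collection (administration of surveys) and mechanism for seeking feedback".

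Section 7.1.6 provides for at least two champions in each intervention SME and none in control SMEs. Under the screening procedure in section 8.1.9, "the local collaborator and champions (intervention sites) at each of the participating SME organisations will disseminate study promotional material (invitation letter" and information sheet, at least 7 days before recruitment opens. Individual consent follows. Section 9.1.2 places the baseline questionnaire directly after consent.

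Section 8.1.4 accepts that "it is not possible to blind participants in the LEOs and SMEs to their group allocation". Its sentence on timing reads "Companies will be informed of the allocation soon after consenting for their involvement in the study prior to consent", which cannot be followed as written.

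Section 8.1.10 lets employees who did not consent use the intervention and be invited into the 6- and 12-month surveys. Section 9.3 estimates the effect as a group-by-time interaction in a two-level model.

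**The concern.** Randomising SMEs makes the SMEs comparable. It makes the respondents comparable only if they are identified in the same way in both arms, without knowledge of allocation. Here the recruiters and employees can know the arm. The intervention arm also has at least two extra people handing out invitations, and their role is to promote the services. The primary outcome, UWES work engagement, is self-reported.

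Three things could follow:

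- Different kinds of employee may join in the two arms.
- Intervention employees may answer the baseline in anticipation of a benefit.
- People may enter the intervention arm after exposure, with no baseline value at all.

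The sample-size text in section 8.1.6 assumes one uniform response rate across SMEs. Unequal recruitment effort by arm works against that assumption. Section 8.1.4, which deals with avoiding bias, covers how SMEs are allocated but not how individuals are recruited afterwards.

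**Working it through.** **Order of events.** The order does not depend on the unclear sentence in section 8.1.4. A champion can exist only once an SME has been allocated to intervention (7.1.6). Champions help send the invitation before recruitment opens (8.1.9). Consent follows the invitation, and baseline follows consent (9.1.2). Employee recruitment and baseline therefore come after allocation. The survey arrangements in 7.1.5, also made after allocation, agree with this.

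**The plan's own figure (8.1.6).** Inputs: means 5.08 and 5.76, SDs 1.40 and 0.86, rho 0.1, average 65 employees per SME, 90% power, two-sided 5%.

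- Difference = 5.76 − 5.08 = 0.68.
- SD = √((1.40² + 0.86²)/2) = 1.162.
- n per arm before clustering = 2 × (1.162 × (1.960 + 1.282)/0.68)² ≈ 61.4, i.e. 62.
- Design effect = 1 + 64 × 0.1 = 7.4.
- SMEs per arm = 61.4 × 7.4/65 = 6.98, i.e. 7.

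The stated seven SMEs per arm is reproduced, and this point does not change it. The 0.68 and 1.162 serve below only as a scale.

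**Possible size of a selection shift.** The following are assumptions, not protocol figures: response is 50% in intervention SMEs (the protocol's ceiling) and 45%, 40% or 30% in control SMEs; the extra intervention responders are 0.25 or 0.5 SD more engaged. Share of extra responders = (0.50 − control response)/0.50. Shift = share × SD difference × 1.162.

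| Control response | Extra share | Shift at 0.25 SD (% of 0.68) | Shift at 0.5 SD (% of 0.68) |
|---|---|---|---|
| 45% | 0.10 | 0.029 (4.3%) | 0.058 (8.5%) |
| 40% | 0.20 | 0.058 (8.5%) | 0.116 (17.1%) |
| 30% | 0.40 | 0.116 (17.1%) | 0.232 (34.2%) |

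These are differences between arms at one time point.

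**Upper bound on the consequence.** Suppose such a shift passed in full into the effect estimate. For a t-test on SME means, SE = 1.162 × √(2 × 7.4/(k × 65)). That gives 0.185 for k = 9 SMEs per arm and 0.160 for k = 12. The nominal 5% two-sided error rate would become:

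| Shift | 9 SMEs per arm | 12 SMEs per arm |
|---|---|---|
| 0.06 | 6.1% | 6.5% |
| 0.12 | 9.4% | 11.1% |
| 0.23 | 21.6% | 28.0% |

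**What the planned contrast removes.** If the extra responders are simply more engaged throughout, the shift enters baseline and follow-up alike and largely cancels in the group-by-time term. Three parts do not cancel: responders selected for how they would change, a baseline moved by knowledge of allocation, and late joiners who contribute follow-up values only.

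**The case against.** The strongest reply is that the analysis compares change, so a stable difference in who responds is mostly harmless. That stands. The shifts in the table are therefore not estimates of bias in the treatment effect.

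The protocol also has real safeguards. All employees in both arms are eligible and invited. The local collaborator acts in both arms. One invitation letter and information sheet are described, with no arm-specific version. The person randomising does not see SME names. Age, sex and job role are collected, so responders can be compared by arm. The stated asymmetry is an extra messenger, not a different message. These points limit the risk, but none conceals allocation when individuals are recruited.

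A reader might go further in two ways that the documents do not support.

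- *The baseline is already contaminated by advertising.* Section 8.1.2 says the services "will be advertised to staff locally in the workplace before and throughout the intervention". That is before the intervention, not necessarily before baseline, and section 6.1 puts baseline before roll-out. Exposure to advertising before baseline is possible but not stated.
- *SMEs can drop out once they know their arm.* Section 7.1.5 says "Following SME director/owner commitment, arrangements will be made with intervention and control arm SMEs to set up the study", and the contracts shared before randomisation are provisional. But the same section requires SME consent before randomisation, and 8.1.4 repeats that order. The later phrase does not show that commitment was absent earlier.

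**Conclusion.** The concern holds as a risk. On the protocol's text, employees are invited, consent and complete baseline after allocation is known, and recruitment effort is greater in the intervention arm. The late-entry route in section 8.1.10 adds selection after exposure. The text describes that route for people who can use the intervention and does not say whether control non-consenters receive a similar invitation.

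The size and direction are unknown, because no response rates by arm are given. The range of about 0.03 to 0.23 points (4–34% of 0.68) rests wholly on the assumed response rates and SD differences, and a stable shift of that size would largely cancel. It would be wrong to quote any one of these values as the bias. What remains is selection on expected change, an anticipation effect at baseline, and late joiners without a baseline. None of these can be sized from the documents, and analysis cannot reliably recover who would have joined without knowledge of allocation.

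**What to change.** 1. In section 8.1.9, delete champions from the invitation step. Use the local collaborator and the same arm-neutral invitation in both arms. This costs only a wording amendment.
2. Where feasible, close employee consent and baseline in each randomisation batch before allocation is released to the SMEs. Start champion promotion and service advertising only after baseline closes. SME consent and workforce data already precede randomisation, so the pairing is unaffected.
3. State that the primary analysis uses employees who consented at baseline, with those joining at 6 or 12 months added in a sensitivity analysis. Report response rates and responder characteristics by arm.
4. Rewrite the sentence in section 8.1.4 on when companies learn their allocation, naming whose consent is meant each time.

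Item 2 carries the main cost: a delay of a few weeks per batch, and a longer gap between baseline and roll-out, because package tailoring and champion recruitment and training follow allocation. That must fit 18 months of follow-up within an award ending in November 2027. If it cannot, items 1, 3 and 4 still remove the difference in invitation channel and keep late joiners out of the primary comparison, but employees would still be recruited with allocation known.
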